
Purpose and Knowledge to be Gained
	
 • The purpose the research is to determine the rates of undiagnosed and uncontrolled hypertension at a population level, as well as changes in clinical practice following the introduction of the new ACC/AHA Hypertension Guidelines, develop new metrics to assess blood pressure control and to test the validity and responsiveness of those metrics in a pilot study. • Results from this work will further our understanding of the size and characteristics of the undiagnosed and uncontrolled hypertensive population. Such information is vital to developing systems to adequately engage these individuals in care, the first step in controlling their disease. Further, understanding how long it takes for these individuals to be connected with an appropriate provider and have their hypertension controlled lays the framework for future work to help decrease delays and minimize variation. A pilot study will offer vital insight into the responsiveness of our newly created care measures and provide pilot data for a proposed larger study. • Additionally, a separate pilot study and interviews will provide important information regarding potential interventions to increase adherence to blood pressure medications. These findings will further our understanding of the types of interventions that can be best utilized in addressing uncontrolled hypertension.

Research Procedures
	
 • The primary research procedures for Aims 1, 2 and 3A are a retrospective review of blood pressure levels for outpatients in the Cedars-Sinai system before and after the introduction of the new clinical guidelines. • Aim 3B is a pilot study to assess the use of home blood pressure monitoring linked to the electronic medical record. This is a prospective intervention of an already approved device, which is compatible with the Cedars-Sinai electronic medical record system and promoted on the Cedars-Sinai website. Study participants for this feasibility study will only include patients already under the care of the PI. • Aim 4A involves conducting interviews discussions to understand the feasibility and implementation of an intervention to increase medication adherence. Participants in the interviews will include current patients who are taking hypertension medications as well as clinic staff. • Aim 4B is a pilot study to evaluate the feasibility, acceptability, and efficacy of an intervention to increase medication adherence involving text message reminders and small incentives for adherence to pill-taking routines.

Subject Population
	
 • For Aims 1-3: All patients seen at least twice in a 12-month period at any Cedars-Sinai outpatient facility • For Aim 4A: All patients with hypertension currently taking hypertension medication and clinic staff • For Aim 4B: All patients with hypertension taking hypertension medication

Duration	
 • For Aims 1, 2 and 3A, all data is retrospective, using already available data collected during routine care. The data to be utilized was collected as part of clinical care from 1/1/2012 through 3/30/2019. • For Aim 3B, prospective data collection will occur during a 9 week period, beginning at the time of patient enrollment. • For Aim 4A, interviews will last one hour on regular clinic days. • For Aim 4B, prospective data collection will occur during a 9 month period, beginning at the time of patient enrollment.
----------	--

GENERAL INFORMATION

CSMC Co-Investigators	
[name], MS [name]
 
[name] [name]

Sponsor/Funder	NIH/NHLBI
Collaborating Institutions Involved in the Research	
RAND Corporation [name]

1.0 BACKGROUND, RATIONALE

Routine ambulatory care visits with diverse clinical specialists represent critical missed opportunities to identify and treat patients with undiagnosed or under-treated hypertension. Hypertension is one of the most important cardiovascular risk factors in both its prevalence and the severity of its consequences.¹ Decades of laboratory and clinical studies have demonstrated a clear link between hypertension and devastating cardiovascular events including stroke, myocardial infarction and renal failure.²⁻⁸ Despite the clear risk, half of hypertensive individuals have blood pressures that exceed current standards for control (<130/80), including nearly 20% of hypertensive individuals who have not yet been given a diagnosis.^{1,9} The high rates of undiagnosed and uncontrolled hypertension appear largely due to lack of recognition or insufficient action by clinicians and health systems, rather than lack of access to care: 82% of individuals with uncontrolled hypertension have a routine place of care and nearly two thirds had at least two ambulatory care visits in the past year.¹⁰ Blood pressure is routinely documented during most ambulatory visits, even in specialty clinics like ophthalmology and orthopedics. Moreover, electronic medical record systems (EMRs) have been widely adopted in outpatient clinics,¹¹ and EMR data that is routinely recorded during clinical encounters can accurately identify patients with undiagnosed or uncontrolled hypertension.¹²⁻¹⁶ This means that health systems already have the data and technical expertise needed to identify patients with undiagnosed and undertreated hypertension. However, few health systems leverage these resources, probably because the feasibility and benefits of doing so have not been demonstrated.

As such, our proposed research program will leverage the capabilities of the EMR to in the detection and treatment of uncontrolled hypertension. Via a future NHLBI-funded K23 Career Development Award, we will achieve two long-term goals. First, we will demonstrate how health systems can use the EMR for the surveillance and detection of undiagnosed and under-treated hypertension. Second, we will develop and test health system-based interventions aimed at reducing the time that hypertensive patients spend without a diagnosis, intensified treatment, or optimal control. We plan to use

the Cedars-Sinai Health System as a laboratory for this research, including both the Medical Delivery Network and the offices of private practitioners who use the Cedars-Sinai EMR.

Additionally, we will perform a pilot study to assess the feasibility of using the EMR to decrease delays in obtaining blood pressure control. Obtaining optimal blood pressure control has linked to a higher number of in-person clinic appointments.¹⁷ With the expansion of wearable devices, the ability to track blood pressure outside of the clinical setting has increased, creating the potential to eliminate this barrier.^{18, 19} Cedars-Sinai allows for clinical data, including blood pressure, to be uploaded directly to the medical record, making this information instantly visible and actionable for providers. We will conduct a pilot study using EMR linked remote blood pressure monitoring devices, in conjunction with clinical pharmacist interventions to assess for a decrease in the time to blood pressure control.

Finally, we will perform an additional pilot study to assess feasibility, acceptability, and preliminary efficacy of daily text messages and incentives to support hypertension medication adherence. Medication non-adherence contributes to suboptimal blood pressure control and increased cardiovascular risk over time.^{20, 21} Routines determine over 40% of all behavior and supporting their formation may offer an effective, low-cost and novel way to increase hypertension adherence. One successful routinization intervention is to anchor, or pair, a new behavior to an existing routine, such as brushing teeth or eating breakfast.²²⁻²⁴ However, existing routinization interventions typically target participants with high intrinsic motivation.²⁵⁻²⁹ Behavioral economics (BE) suggests that small rewards and reminders can support routinization for all patients, including those with low motivation.³⁰⁻³² We will conduct a pilot randomized controlled trial (RCT) using daily text messages and small incentives to evaluate potential improvements in medication adherence, and will conduct interview discussions to determine feasibility and acceptability of these incentives.

2.0 STUDY OBJECTIVES

The objective of the currently proposed study is to provide pilot data for this longer-term research program. In preparation for this K23 application, we must achieve the following aims.

Aim 1: Determine the cross-sectional prevalence of undiagnosed and uncontrolled hypertension within the Cedars-Sinai Health System, as well as the patient, physician, and clinic characteristics associated with these outcomes. This will document the presence and extent of problems at this institution and reveal which populations and settings are most affected, providing insights that can be used to develop and implement future interventions.

Aim 2: Develop and pilot test new time-to-care and time-to-control measures. These measures will evaluate (1) how long it takes from when evidence exists in the EMR that patients meet criteria for hypertension before clinicians document a diagnosis and initiate treatment, (2) how long evidence exists that control is suboptimal before clinicians intensify treatment, and (3) how long each of these conditions exists before goal blood pressures are achieved. We plan to use these new measures in our future work because we expect them to be more responsive to changes in care than cross-sectional measures of control would be, and because they include both care processes (i.e., did clinicians do the right things) and outcomes (i.e., were clinical goals achieved), making it possible to distinguish whether suboptimal control is due lack of recognition, lack of action (e.g., clinical inertia), or insufficient action (e.g., suboptimal adjustment of antihypertensive medications).

Aims 3A and 3B: Aim 3A – Assess the validity, responsiveness, and potential utility of the new time-to-care and time-to-control measures. To assess validity, we can examine whether performance on the new measures is associated with performance on cross-sectional measures of blood pressure control. To assess responsiveness and potential utility, we can examine how performance changes with clinical practice. For example, the introduction of the 2017 ACC/AHA guidelines represented a marked change in the standard of care for hypertension in terms of criteria for diagnosis and blood pressure goals. If the

prevalence of undiagnosed and uncontrolled hypertension at Cedars-Sinai is high, slow uptake of these new standards may be one explanation. However, another potential explanation is the much greater level of effort needed to attain the lower blood pressure goals. If clinicians are recognizing uncontrolled hypertension and initiating or intensifying treatment, we would expect the time-to-care measures to exhibit stable performance after 2017 while performance on the time-to-control measures and cross-sectional control rates would decline.

We will also examine how performance on the time-to-care and time-to-control measures varies based on the setting in which blood pressure is measured. If we find that that performance on these time-to-care and time-to-control measures as well as control rates are better in Primary Care, Internal Medicine, Nephrology, or Cardiology clinics than in other specialty and subspecialty clinics, this would suggest the EMR may be a useful for the screening and detection of patient populations that would benefit from efforts to make a diagnosis and initiate or intensify treatment.

Aim 3B – We will perform a pilot study of the new time-to-control measure’s responsiveness to more intensive blood pressure monitoring and intervention. This pilot will provide a subset of uncontrolled hypertensive patients with home blood pressure monitors linked to the EMR at Cedars-Sinai. This information will be monitored and acted upon weekly, allowing for a more rapid titration of medical therapy. A decrease in the time-to-control measure of blood pressure management would be a preliminary finding consistent with measure responsiveness.

Aims 4A and 4B: Aim 4A – We will conduct interview discussions to explore feasibility and acceptability of text message reminder and incentives for blood pressure medication adherence. These interview discussions will involve both patients and providers and will allow for a better understanding of existing routine behaviors that support pill-taking, appropriate messaging for text message reminders, and how to best implement the intervention.

Aim 4B – We will perform a pilot study to measure the feasibility, acceptability, and efficacy of interventions designed to increase blood pressure medication adherence. This pilot RCT will include a subset of uncontrolled hypertensive patients who will receive daily text messages and/or a small incentive related to blood pressure medication adherence, depending on the intervention group, with MEMS-cap devices to allow for automated electronic assessment of patient medication use. A subgroup of participants will document their experience with taking medication using a secure video platform.

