3.0 STUDY POPULATION

3.1 SELECTION OF THE STUDY POPULATION

1. For Aims 1, 2 and 3A, data for patients will be obtained from the Cedars-Sinai electronic medical record.
2. For Aim 3B, a sample of 10 patients seen in the Hypertension Center or Women’s Heart Center clinic, who meet the pre-defined criteria for uncontrolled hypertension at the time of data procurement, will be selected.
3. For Aim 4A, a sample of 20 patients seen in the Hypertension Center or Women’s Heart Center as well as 7 medical providers will be selected to inclusion in interview discussions.
4. For Aim 4B, a sample of 60 patients hypertensive patients taking antihypertension medications will be selected.

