3.2 INCLUSION CRITERIA

1. Patients seen at any Cedars-Sinai outpatient clinical (including OB/GYN) from 1/1/2012 through 3/30/2019.
2. Age >18 years at any time during the study period
3. Patients with blood pressure recordings in the EMR

4. At least 2 outpatient clinic visits in a 12-month period
5. Additional inclusion criteria for Aim 3B only:
 - Patients must be seen in the Hypertension Center
 - Patients must have a smartphone compatible with My CSLink, the Cedars-Sinai mobile health application (any smartphone running iOS or Android operating software)
6. Additional inclusion criteria for Aim 4A only:
 - Patients must be currently prescribed hypertension medication.
 - Providers and clinic staff must have been employed at clinic for 12 months.
7. Additional inclusion criteria for Aim 4B only:
 - Patients must be initiating or already taking antihypertension medication.

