3.4 SUBJECT SCREENING AND ENROLLMENT

Subject screening applies only to Aim 3B, Aim 4A, and Aim 4B.

Aim 3B:

- a. Patients to be included in Aim 3B will be identified by physicians in the Hypertension Center, as part of his clinic panel.
- b. Eligible patients must have diagnosed hypertension but are not yet controlled (SBP<130 and DBP<80). Patients may already be on medications for hypertension.

Aim 4A:

- a. The research coordinator will monitor the clinic schedule for potentially eligible patients. The nurse manager of the clinic will be notified of the offer for physicians and nurses in the clinic to participate in interviews. Recruitment will occur for staff via institutional email.
- b. Eligible patients must currently be on hypertensive medication. Eligible staff must have been employed at the clinic for 12 months.

Aim 4B:

- a. The research coordinator will monitor the clinic schedule for potentially eligible patients together with clinic providers and staff. We will consent and enroll 1-2 patients/day during the 3-month recruitment period.
- b. Eligible patients must have hypertension and be initiating or already taking antihypertension medication.

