3.5 SUBJECT RECRUITMENT

Subject recruitment applies only to Aim 3B, Aim 4A, and Aim 4B.

Aim 3B:

1. The Hypertension Center physicians will identify patients in his clinic who meet criteria for uncontrolled hypertension.
2. If the patient is agreeable, the clinical pharmacist will be contacted to complete enrollment. Enrollment will be completed during the same clinic visit at which the patient was identified, above. Informed consent will be obtained at that time. Further details of the enrollment process are detailed in Section 4.0, under ‘Intervention.’

Aim 4A:

1. The research coordinator will identify patients with hypertension that meet inclusion criteria via the clinic schedule. Clinic staff, including physicians and nurses, will be contacted via institutional email to offer participation in interviews. All emails will be internal and not used for contacting patients.
2. If the patient is agreeable, the research coordinator or physician will be contacted to complete enrollment. Enrollment will be completed during the same clinic visit at which the patient was identified, above. Informed consent will be obtained at that time.

Aim 4B:

1. The research coordinator will identify patients with hypertension initiating hypertension treatment via the clinic schedule.
2. All patients will receive written consent materials explaining the purpose and contents of the study. All interview members will also receive written consent materials explaining the purpose and contents of the study. We will explain clearly that participation in a specific intervention group is not a choice but based on random assignment (the Human Subjects Protection document elaborates on IRB-related issues). We will show all potential participants the MEMS device and explain its purpose. Each will receive \$50 USD for participation in each study assessment (baseline, month 1, month 2, month 3 and month 9).
3. Participants who are randomized into the incentive cohort and comply to greater than 80% medication adherence will be eligible to participate in a drawing every month for the first three months of intervention. The drawing will include a prize of either \$0, \$25, or \$50.
4. All participants will receive a parking validation.

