The pilot RCT study would include 60 randomly selected hypertensive patients on hypertension treatment who may receive text message reminder and/or incentives, depending on the treatment group to which they are randomly assigned. Participants will be randomly assigned to one of three treatment groups: the control group (receives care as usual plus information on importance of establishing pill-taking routines), the message group (receives daily text messages for 3 months reinforcing information on importance of establishing pill-taking routines), or the incentive group (in addition to the same daily text messages as the message group, has a chance of winning small, intermittent rewards for taking medication in accordance with established pill-taking routine). The intervention period will last for 3 months and data monitoring will occur for an additional 6 months post-intervention totaling 9 months. Participants randomized into the incentive cohort will be eligible for a drawing only if they achieve greater than 80% medication adherence. The drawing will take place once a month for the first three months of participation with a chance to receive \$0, \$25, or \$50. Outcome measures include electronically measured medication adherence, hypertension control, adherence to established pill-taking routine, and feasibility and acceptability of intervention. We hypothesize that patients in the message and incentive groups will have higher medication adherence and hypertension control compared to the control group, and that patient in the incentive group will show greater adherence to established their pill-taking routine compared to the message and control groups.

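### The Aim 4B objective names uncontrolled patients, but the Aim 4B eligibility criteria set no blood pressure limit, so the blood pressure control outcome mixes attaining control with keeping it

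*Protocol*

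**What the plan says.** The Protocol describes the Aim 4B population in several places.

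- **Section 2.0, objectives:** "This pilot RCT will include a subset of uncontrolled hypertensive patients".
- **Section 3.2, inclusion:** "Patients must be initiating or already taking antihypertension medication".
- **Section 3.4, screening:** "Eligible patients must have hypertension and be initiating or already taking antihypertension medication".
- **Section 3.5, recruitment:** "The research coordinator will identify patients with hypertension initiating hypertension treatment via the clinic schedule".
- **Synopsis, subject population:** "For Aim 4B: All patients with hypertension taking hypertension medication".
- **Section 3.1:** "a sample of 60 patients hypertensive patients taking antihypertension medications will be selected".
- **Section 4.0:** "The pilot RCT study would include 60 randomly selected hypertensive patients on hypertension treatment".

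The Aim 4B exclusions in section 3.3 concern capacity to consent and owning a cell phone. Section 4.0 defines control as a pressure below 130/80.

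Hypertension control is an Aim 4B outcome in section 4.0 and part of the first Aim 4B hypothesis in section 7.1. The SAP names adherence and blood pressure control as the primary and secondary outcomes. It adjusts for characteristics found to separate the groups at baseline, and plans separate analyses by age and sex.

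**The concern.** The objective describes a trial in patients who are not at goal. The criteria that govern enrolment would admit patients who are. What the control outcome measures depends on which of these applies.

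- If everyone is uncontrolled at entry, control at follow-up is new attainment of goal. Regression to the mean will raise it in every arm.
- If controlled patients also enter, it is a blend of attainment and maintenance, in proportions that the plan does not set.
- If patients are starting treatment, it also reflects the start of the drug, and there is no earlier pill-taking routine for that drug.

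Nothing in the SAP separates these. Baseline control status enters a model only if the arms happen to differ on it, and no result is planned by baseline control or by new versus established treatment. Section 7.2 gives the purpose of the pilot as data to support an R01. A difference in control rates from an undefined mix is hard to carry forward to a trial in either population.

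**Working it through.** **Step 1. Compare the texts.**

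| Place in Protocol | Uncontrolled required? | Treatment status |
|---|---|---|
| 2.0 objectives | Yes | Not specified in the population phrase |
| 3.2 and 3.4 criteria | No | Starting or already on |
| 3.5 recruitment | No | Starting |
| Synopsis, 3.1, 4.0 | No | Taking or on |

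The clear conflict is between 2.0 and the criteria in 3.2 and 3.4. Section 3.5 and the remaining wordings add a second, looser inconsistency about treatment status. For Aim 3B, by contrast, section 3.4 does state a control criterion: "Eligible patients must have diagnosed hypertension but are not yet controlled (SBP<130 and DBP<80". Aim 4B has no such line.

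**Step 2. Is there a planned figure to reproduce?** No. The 60 patients are justified in section 7.2 by pilot purpose, without alpha, power, rates or effect size. What follows is an illustration.

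**Step 3. Inputs.**

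- Total 60 and three arms: Protocol 4.0.
- Pooled message and incentive groups against control: SAP, Specific Aim 2a.
- Allocation 1:1:1, hence 40 versus 20: assumed, as no ratio is stated.
- Two-sided alpha 0.05: assumed.
- Chance that an uncontrolled patient reaches control, q: 0.60 active, 0.30 control (assumed).
- Chance that a controlled patient stays controlled, s: varied (assumed).
- Share uncontrolled at entry, f: 1 or 0.5. The value 0.5 echoes section 1.0, which says that half of hypertensive individuals are above 130/80. The true share in these clinics is unknown.

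**Step 4. Formulas.**

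Control rate in an arm: p = (1 − f)·s + f·q.

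Power = Φ[(d − 1.96·SE0)/SE1], where d is the difference between the arms, SE0 uses the pooled proportion and SE1 the separate proportions.

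**Step 5. Results.**

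With f = 1: d = 0.60 − 0.30 = 0.30 and the pooled proportion is (40 × 0.60 + 20 × 0.30)/60 = 0.50.
SE0 = √(0.25 × (1/20 + 1/40)) = 0.137.
SE1 = √(0.21/20 + 0.24/40) = 0.128.
Power = Φ[(0.30 − 0.268)/0.128] = Φ(0.246), about 60%.

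With f = 0.5 and s = 0.85 in both arms: active 0.425 + 0.30 = 0.725, control 0.425 + 0.15 = 0.575, d = 0.15. Power is about 22%.

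| Uncontrolled at entry | s, active vs control | Control rate, active vs control | Patients | Power |
|---|---|---|---|---|
| All | not applicable | 60% vs 30% | 40 vs 20 | about 60% |
| Half | 85% vs 85% | 72.5% vs 57.5% | 40 vs 20 | about 22% |
| Half | 90% vs 80% | 75% vs 55% | 40 vs 20 | about 35% |
| Half | 95% vs 75% | 77.5% vs 52.5% | 40 vs 20 | about 51% |
| Half, uncontrolled subset only | not applicable | 60% vs 30% | 20 vs 10 | about 33% |

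Other assumed attainment rates (0.20 vs 0.40, 0.20 vs 0.50), with s equal in both arms at 0.85 or 1, were also tried. Over all the sets, power runs from 33% to 62% when all are uncontrolled, and from 11% to 25% when half are.

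**The case against.** Several points on the other side stand.

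- **The criteria agree with each other.** Sections 3.2 and 3.4 use the same rule and would probably govern enrolment. A reader might infer from section 3.5 a third population limited to patients starting treatment. The text does not support that: it is a recruitment step and contains no word of restriction.
- **The omission may be deliberate.** Aim 3B has an explicit control criterion and Aim 4B does not, so the criteria may be what was meant and the objective loosely worded. That supports reconciling the texts; it does not remove the conflict.
- **Controlled patients are informative.** One might infer that patients already at goal add nothing, or that power must fall to 22%. They can lose control, and an adherence intervention may help to prevent that. The 22% rests on no maintenance effect; with one of 10 to 20 points the figure is 35% to 51%.
- **The comparison stays fair.** A reader might infer bias. Randomisation protects the contrast between arms whoever is enrolled.
- **The hypotheses and the SAP do not speak of uncontrolled patients.** They refer to treatment groups and participants, so it does not follow that results would be claimed for uncontrolled patients alone.
- **Power is a limited yardstick.** This is a pilot without a power target, and control is one of several outcomes.

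What remains is that the objective and the criteria describe different samples, and the SAP has no means of telling attainment from maintenance.

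**Conclusion.** The concern holds as an inconsistency between the Aim 4B objective and the Aim 4B criteria, with looser disagreement elsewhere about treatment status. As written, patients below 130/80 may enter, so the control outcome blends two quantities and the sample need not fit the stated objective. The harm is to interpretation, precision and planning of the later study, not to the validity of the randomised comparison.

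Its size cannot be fixed from the documents. On the assumed 60% versus 30% attainment, power of about 60% with all patients uncontrolled becomes about 22% to 51% if half are already controlled, depending almost wholly on whether the intervention also helps to maintain control. These figures further assume 1:1:1 allocation, two-sided alpha 0.05 and no dropout. The stronger readings, of bias or of a certain fall to 22%, are not supported. The correction is worth making before analysis.

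**What to change.** 1. Reconcile the Protocol synopsis and sections 2.0, 3.1, 3.2, 3.4, 3.5 and 4.0 into one Aim 4B eligibility statement. It should say whether a baseline blood pressure criterion applies, and whether patients starting treatment, patients already on it, or both may enter. The choice belongs to the sponsor.
2. If controlled patients may enter, pre-specify in the SAP that blood pressure control is analysed in all 60 with adjustment for baseline blood pressure or baseline control status, whether or not the arms look unbalanced on it.
3. In that case, also report control descriptively, with numbers and intervals by arm, among participants at or above 130/80 at baseline. Baseline blood pressure is already listed in Protocol Table 4.

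The cost is a Protocol clarification and a short SAP addition; no new visits, data or patients are needed. The drawback is that the uncontrolled-at-entry report is small: 20 versus 10 patients if half are uncontrolled, with power of about 33% on the assumptions above. It should be read as description and not as a test.
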